1.0 Introduction

The overall goal of this study is to minimize negative consequences of Alzheimer's disease and related disorders (ADRD) diagnosis by enhancing the support systems of affected families through the provision of the Options Counseling-Health Education (OC-HE) intervention.

The primary objective is to evaluate the impact of OC-HE intervention on caregivers (caregiver burden) and patients (use of emergency care). The secondary objective is to evaluate the impact of the program through the proposed mechanisms of influence, enhanced social network composition (e.g., network size) and functioning (e.g., social support). In addition, we will assess intervention feasibility and acceptability to better understand intervention impacts and to inform future implementation from the perspectives of the participants, OC-HE interventionist, clinical care staff, and administrator at the Area Agency on Aging.

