2.0 Brief Overview of the Study Protocol

The study protocol, presented as an appendix, provides a scientific rationale of the proposed investigation. A brief overview of the study protocol is presented here.

This is a Stage 1 intervention study based on the NIH Stage Model for Behavioral Intervention Development. We aim to enroll 106 family members of individuals newly diagnosed with dementia (PWD); 53 in each of the two group. Participants will be Iowa residents who provide support to a PWD who received diagnosis within the past 6 months. We will recruit adults ages 18 years and older, both males and females, who are not limited cognitively or physically to consent to study participation, to participate in interviews, and to receive intervention.

All participants will be recruited through the University of Iowa Hospitals and Clinics. Three clinics have agreed to facilitate the recruitment: Geriatric Assessment Clinic, Memory Disorder Clinic, and Adult Psychiatry Clinic. Clinical staff members will identify potential participants and either obtain permission for research staff to contact them or provide study and contact information of the research staff for them to contact us. We will not recruit participants outside of the United States. After consenting and completing the baseline interview, participants will be randomly assigned to either OC-HE intervention group or usual care control group.

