The intervention consists of two parts, Options Counseling (OC) and Health Education (HE). The OC part includes family assessment, counseling and provision of emotional support, access assistance, and development of independent-living plans (care plans) using the Iowa's Heritage Area Agency on Aging database. The Options Counselor is trained to use motivational interviewing techniques to develop family care plans, provide emotional support, and connect families to available services and programs in the community. The HE part includes post-diagnosis family education using the 7-module health education toolkit developed specifically for this study based on the literature and expert reviews. OC-HE will conduct initial assessment to determine educational needs within 2 weeks of participant's randomization into the intervention group and develop initial care plan; and will conduct 5 monthly follow-up calls to adjust the care plan and provide educational components appropriate at each point. This intervention aims to create direct links between the medical clinics, home and community-based services (HCBS), and family.

Participants assigned to the usual care control group will participate in baseline, as well as 3- and 6-months

follow-up surveys. Those in usual care group will receive a general informational brochure from the Alzheimer's Association, and will be given an option of receiving a call from their local Options Counselor after completing the 6-month survey.

Study duration is about 18 months. We aim to start participant enrollment in August, 2019, complete recruitment by September, 2020, and complete data collection by March 2021. Each participant will be enrolled in this study for about 6 months from enrollment to final interview.

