5.0 Recruitment and Retention

Sample

Between June 2015 and May 2016, the 3 UIHC clinics served about 17,500 people with dementia and 657 were newly diagnosed. Power calculations were performed under the assumption of reaching about 12% of newly diagnosed individuals, 106 people; assuming a 25% attrition rate, this will lead to 80 people (40 per group). This will give us about 84% power to detect a 4-point decrease in Caregiving Burden at each 3-month period. Assuming some people may not meet the inclusion criteria, we anticipate screening around 138 potential participants including women and minorities to reach target enrollment size.

Participants

Family participants/caregivers will be family members or friends (e.g., biological and non-biological relatives, friends) who likely will coordinate care and support for the individual who received dementia diagnosis at one of the three participating clinics: Memory Disorder Clinic (Neurology), Geriatric Medicine Clinic (Family Medicine), and Adult Psychiatry (Psychiatry) at the University of Iowa Hospitals and Clinics (UIHC). Potential family participants/caregivers will be referred by the clinical care team members by reviewing EMR in EPIC and identifying patients who have been diagnosed with Alzheimer's or other dementia within the past 6 months. All participants will be asked to participate in a baseline survey and follow-up surveys at three and six months regarding their sociodemographic characteristics, Home and Community-Based Services (HCBS) use and knowledge, caregiving self-efficacy, caregiving preparedness, social support and networks, and their physical and psychological well-being. After completing the baseline, participants will be randomized into either the Options Counselor-Health Educator (OC-HE) intervention group or the standard care (control) group. Participants in the OC-HE intervention group will receive intervention after completing the baseline survey. All consents and interviews will be conducted by the trained research staff from the University of Iowa. Prior to enrolling

participants for the randomized trial, three to five individuals who have family members with dementia diagnosis will be asked to help with pilot testing program materials by providing feedback on the program contents and implementation procedures.

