6.1 HIPAA Authorization

Because we have access to health data through the electronic medical record and because we are collecting some data through the electronic medical record (MoCA and use of medical services), all research team members have completed HIPAA training through the University of Iowa Hospitals and Clinics Human Resources.

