7.0 Study Intervention

Intervention Description

The intervention consists of two parts, Options Counseling (OC) and Health Education (HE). The OC part includes family assessment, counseling and provision of emotional support, access assistance, and development of independent-living plans (care plans) using the Iowa's Heritage Area Agency on Aging database. The HE part includes post-diagnosis family education. Options Counselor (OC) is trained to implement these tasks through using motivational interviewing techniques. We developed seven modules of the HE toolkit based on an extensive literature review on unmet needs of families receiving diagnosis of dementia, experiences of Options Counselors, and expert reviews by experienced staff members at the local Alzheimer's Association.

Through the OC-HE intervention, we aim to minimize caregiver burden through enhancing the social support network system of the participants by providing direct access to community-based programs as well as to the Options Counselor who provides emotional support and instructions on how to form strong support networks. Lower burden and better support are associated with better patient outcomes, thus, we will also evaluate whether PWDs whose caregivers receive OC-HE intervention would use emergency or urgent medical services to a lesser extent.

Each intervention encounter will occur in a setting of the participant's choosing. Typically, the initial visit is in the home of the participant (caregiver) and involves just the participant and the Options Counselor. However, the participant is able to invite whomever they choose to come to the meeting, including the PWD. The participant may choose to have the meeting at different location if the person they are caring for lives with them and they do not want to introduce the information in this manner. Although it is preferable to have this initial visit in person, the meeting can be done via phone call or virtually through a web-conferencing if participant desires so. Normally, each home visit, or face to face meeting, lasts around 1.5 hours, however, because of the addition of the Health Education component in this particular study, we

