Perceived support: At each assessment, the participants report their relationships with each network member (e.g., who provides emotional support? Who helps you provide direct care? Who participates in discussions to make care decisions) to assess network functions. Levels of support can be determined by taking an average support levels among family, non-family, professionals, for each type of support (e.g., emotional, informational, instrumental, direct care, care decision making).

Social engagement: Participants identify network members with whom they engage in social activities to assess how the network functions as a context for social engagement.

At the patient level, generalized linear models (GLM) with an appropriate link function (e.g., the identical link for continuous outcomes, the logit for dichotomous outcome, and the log link for count outcomes) will be used to assess associations between the caregiver and patient outcomes and network composition and network functions. In particular, a set of the composition measures will be considered as independent variables to each outcome in a GLM. Similarly, a set of network functions (e.g., change between baseline and 3-month) will be included to assess the association with each outcome at 6-month in a GLM.

Follow-up analyses

Once we identify network functions that are important for the caregiver and patient outcomes (e.g., emotional support, provision of direct care support) are identified in the main analyses, we will be able to conduct dyad-level analyses to identify the whole network characteristics (e.g., network size, homogeneity), network member characteristics (e.g., gender, relationships, live locally), as well as relationship characteristics (e.g., presence of trust, duration of relationship) that may contribute to such positive network functions.

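### The supplied SAP neither contains nor cites a comparison of OC-HE with usual care on caregiver burden or emergency-care use, which is the trial's primary objective

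*SAP*

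**What the plan says.** Protocol section 1.0 states: "The primary objective is to evaluate the impact of OC-HE intervention on caregivers (caregiver burden) and patients (use of emergency care". The next sentence begins: "The secondary objective is to evaluate the impact of the program through the proposed mechanisms of influence", and goes on to network composition and functioning. Section 7.0 restates the patient outcome as a question about the intervention: "we will also evaluate whether PWDs whose caregivers receive OC-HE intervention would use emergency or urgent medical services to a lesser extent". Sections 2.0 and 8.0 randomise 1:1 to OC-HE or usual care, 53 per arm, and section 5.0 expresses power in terms of caregiving burden. On service-use data, section 6.1 says "we are collecting some data through the electronic medical record (MoCA and use of medical services".

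The SAP, under Revised Data Analysis Plan, defines network composition, perceived support and social engagement. It then specifies two families of models.

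- Patient level: GLMs with a link suited to a continuous, binary or count outcome "will be used to assess associations between the caregiver and patient outcomes and network composition and network functions". The predictors are either a set of composition measures or a set of network functions, for example their change from baseline to 3 months. The network functions are related to outcomes at 6 months.
- Dyad level, under Follow-up analyses: logistic GEE models of whether a network member gives a particular kind of support. Respondent and member covariates are listed as examples.

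**The concern.** A trial randomised 1:1 to learn whether a programme reduces burden and emergency-care use needs an analysis that contrasts the two arms on those outcomes. The SAP never names arm as a predictor and never states a contrast between OC-HE and usual care. An analyst who followed it exactly would report how outcomes vary with network measures. There would be no estimate, interval or test for the effect of assignment on either primary outcome.

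The secondary objective is affected too. To say that a programme acts through networks, one must first show that it changes networks, and the plan has no model for that step. The comparison that randomisation protects would go unreported, while associations that it does not protect would carry the conclusions.

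**Working it through.** **1. The protocol's own figures.** Section 5.0 says "assuming a 25% attrition rate, this will lead to 80 people (40 per group". Check: 106 × (1 − 0.25) = 79.5, which rounds to 80, or 40 per group. The stated power of about 84% for a 4-point decrease in burden cannot be reproduced, because no SD, alpha or test is given. It can only be solved backwards. Assume a two-sided 0.05 comparison of two means (normal approximation) with n = 40 per group:

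SD = Δ / [(z₀.₉₇₅ + z₀.₈₄) × √(2/n)] = 4 / [(1.960 + 0.994) × √(2/40)] = 4 / 0.661 = 6.05.

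If a 4-point decrease in each 3-month period means 8 points by 6 months, the SD doubles to 12.1. These figures show that a burden analysis with two groups was in mind. They do not supply a model, and they do not bear on what the SAP contains.

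**2. Objectives against specified models.**

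| Question in protocol 1.0 | Model it needs | What the SAP specifies |
|---|---|---|
| Effect of OC-HE on burden | Burden with an arm term | Caregiver outcomes on network measures; arm not named |
| Effect of OC-HE on emergency care | Emergency use with an arm term | Patient outcomes on network measures; arm not named |
| Effect through networks, first link | Network change with an arm term | None |
| Effect through networks, second link | Outcome on network change, with arm in the model | 6-month outcomes on baseline-to-3-month change; arm not named |

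**3. Search of the whole SAP text.** Words for randomisation, arm, control, usual care, standard care, comparison, burden, emergency, urgent and primary each occur 0 times. Group occurs once, for age groups. Difference occurs once, for network change over time. The missing arm contrast is the finding. The absence of the words burden and emergency proves little, because the SAP's general reference to caregiver and patient outcomes can cover both.

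**4. Why the specified models cannot stand in.** Write A for arm, N for network change from baseline to 3 months, and Y for the 6-month outcome. Randomisation protects the contrasts of A with Y and of A with N. The SAP models N with Y.

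- N is measured after randomisation and is not itself assigned. Caregivers whose support grows may differ in other ways that also affect Y.
- If OC-HE moves N and also moves Y by another route, such as education, a model without A shows an N–Y association even if networks are not the mechanism.
- Composition is recorded at baseline and updated at 3 and 6 months, and the SAP does not say which assessment enters the GLM. Baseline composition gives a prognostic association and later composition a post-randomisation one. Neither is an effect of assignment.
- The dyadic covariate lists are examples, so arm is unnamed rather than excluded. Even with arm added, the outcome that the SAP illustrates there is support from a network member, not burden or emergency care.

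**The case against.** The strongest reply is that the file is incomplete. Protocol section 2.0 says: "The study protocol, presented as an appendix, provides a scientific rationale of the proposed investigation". That appendix is not among the documents, and the protocol in hand is the Manual of Procedures. The SAP calls itself revised, which implies an earlier plan. The power statement also shows that a burden analysis by group was contemplated. This stands, and it limits the point to what the supplied SAP contains and cites.

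A second reply is that the SAP may be a revision for the mechanism objective only. Its Mechanisms of Influence section says that mechanisms will be assessed with network measures, and every measure it defines is a network measure. This is a plausible reading, but the SAP does not say that it is so limited or where the primary analysis is kept. It also describes a programme of an initial call and 2 follow-up calls over 3 months, while protocol sections 2.0 and 7.0 describe 5 monthly follow-up calls. An earlier analysis should therefore be cited or restated rather than assumed to carry over. Even as a mechanism plan, it lacks the link from arm to network change.

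A third reply is that the GLM outcomes probably include burden and emergency care. That is fair, but it fills only the left side of the model.

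Finally, this is a Stage 1 study with feasibility aims. That softens the consequence but does not remove the stated primary objective.

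**Conclusion.** The point holds for the SAP as supplied. Of the two primary outcomes, neither has a specified or cited arm comparison, and the mechanism aim has no model of arm on network change. As written, the plan can show neither whether OC-HE works nor whether it works through networks. No corrected number applies. The conclusion assumes that the SAP text is complete; it runs without a visible gap apart from one figure on the title page.

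Three stronger readings are tempting, and the documents do not support them.

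- *The trial never planned, or has dropped, an arm comparison.* The missing appendix and earlier plan may contain one.
- *The SAP promotes the network GLMs to the trial's main analysis.* Its phrase about main analyses appears under Follow-up analyses. There it most naturally separates the patient-level network models from the dyad-level ones.
- *The January 2022 date shows that the plan was written after outcomes were seen.* Section 2.0 planned to "complete recruitment by September, 2020, and complete data collection by March 2021", but that was a schedule. The SAP records pandemic changes, and neither document gives actual dates or says when data were seen.

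**What to change.** If an arm comparison exists in the protocol appendix or the earlier plan, cite or restate it in the SAP as the primary analysis. If it does not, add the following, with participants analysed as randomised:

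- Burden: a baseline-adjusted difference between arms with a 95% CI, from the 3- and 6-month scores.
- Emergency-care use: a GLM with an arm term and a link suited to how the outcome is recorded.
- Mechanism: a model of arm on baseline-to-3-month network change, and arm included in the existing network GLMs.
- Labelling: a statement that the network GLMs are secondary mechanism analyses.

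Date the addition. If outcome data have already been seen, label it as not pre-specified.

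The cost is a few more models, with no new participants or visits. This assumes that burden is scored at baseline, 3 and 6 months, as the power statement implies, and that service use is drawn from the medical record as section 6.1 says. The real downside is that pre-specification may not be recoverable; dating and labelling disclose that but do not cure it.

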12.5 Administrative Forms

Form	Appendix	Description
Participant Identification Code List	R	Used to document the participant's study identification number, name, and other identifying information. Stored separately from research records since it is the link between a study ID and participant's name.
Recruitment Log	C	Used to list participants screened; includes those who fail screening and those who are enrolled. Collects date, age, gender, race, care needs, relationship to PWD, Rural (Y/N), Agreed to participate, Reason for not enrolling, study ID
Phone Call Log	S	Used to log all phone call conversations/follow-ups
Study Personnel	T	Used to list contact information for all study personnel and their specific responsibilities
Heritage AAA Log		Used by the OC, who is an employee at Heritage Area Agency on Aging to log options counseling sessions
Research Log		Extensive Database with points of contact to track participants through the research process
Intervention Log		Database at University of Iowa where the OC-HE tracks options counseling sessions
EPIC		University of Iowa Electronic Medical Record where Care Plans will be uploaded or typed into the "notes"

		section
Participant Contact Form (from Clinic to Research Staff)	U	Used by clinicians to collect contact information about the potential participants so that the Research Manager can contact the interested potential participant
Participant Reimbursement Form	N	Used by the Interviewer to collect information about the participant so that the participant can be paid their \$20 incentive for each interview
Interview Script	V	Used by the interviewer to introduce the study, ask about adverse events, conduct the interview, and end the interview
Adverse Event Form	G	Used by the PI to report Adverse Events
Serious Adverse Event Form	H	Used by the PI to report Serious Adverse Events

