Mechanisms of Influence. The social network framework highlights the importance of enhancing network functions (e.g., social support) on health outcomes. Strong social support networks have been shown to be important for the well-being of caregivers and care recipients, and their ability to remain in the community. The intervention provides families 1) tangible, informational, and emotional support, 2) guidance on building strong support systems and effective communication, and 3) access service linking families directly to community-based resources. Through these activities, we intend to strengthen families' social networks to facilitate successful community living. In our prior study, families considered formal providers as important members of their caregiving support systems, suggesting the important role Area Agency on Aging staff can play in this mechanism. In this study, we are systematically examining the compositional and functional characteristics of social networks, that are theorized to influence patient and family outcomes. We will assess the mechanisms of influence using the social network measures specifically developed for dementia caregiving studies that assess social interactions specific to caregiving in addition to general support. Understanding the mechanisms through which intervention improves outcomes will provide a framework to optimize support for patients and their families across all stages of the illness.

Revised Data Analysis Plan

Network composition: Network members are enumerated based on participation in caregiving activities and provision of support to caregivers at baseline. In 3- and 6-month assessments, participants indicate changes in their networks (e.g., indicate those who are no longer part of support network, add new support providers). We will develop network composition measures including network size and proportion/number of family, non-family/friends, professional providers, live locally, gender, age groups (e.g., same/older/younger generations).

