At the dyadic-level, a logistic regression model will be fitted for each outcome (e.g., presence of emotional support, provision of direct care support) using generalized estimating equations with the exchangeable correlation structure to account for the clustering of the network members within the respondents' networks. Both respondent-level (e.g., gender, relationship to care recipient) and network member-level covariates (e.g., family member of the care recipient, age, whether living locally) will be considered in these models. To assess the impact of changes in network functions, differences between baseline and 3-month network functions (e.g., change in support provision) will be used as independent variables to the outcomes at 6-months.

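### The patient-level network GLMs name no measure of dementia severity, although MoCA is already taken from the record, so severity can be read as a network effect, chiefly in the composition models

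*SAP*

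**What the plan says.** The SAP (Revised Data Analysis Plan) sets out two kinds of patient-level GLM.

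- **Composition models.** Here "a set of the composition measures will be considered as independent variables to each outcome in a GLM". The measures include network size and the share or number of family, friends, professionals and local members.
- **Function models.** Network functions, for example their change from baseline to 3 months, "will be included to assess the association with each outcome at 6-month in a GLM".

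No adjustment covariate is named for either. Covariates appear only for the dyad-level GEE under Follow-up analyses: "Both respondent-level (e.g., gender, relationship to care recipient) and network member-level covariates". They are given as examples, and none is a severity measure.

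Three other statements bear on the point.

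- On who enters the network, the SAP says: "Network members are enumerated based on participation in caregiving activities and provision of support to caregivers at baseline".
- Under Mechanisms of Influence the purpose is put in causal terms: "Understanding the mechanisms through which intervention improves outcomes will provide a framework to optimize support".
- Protocol 6.1 says "we are collecting some data through the electronic medical record (MoCA and use of medical services". The SAP does not mention MoCA.

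**The concern.** Randomisation protects the comparison of arms. It does not protect a regression of outcome on network measures, because caregivers were not allocated to networks. A person with more advanced dementia plausibly draws in more helpers and professionals, and plausibly also causes more burden and more emergency visits. Counting network members by caregiving activity builds part of that link into the exposure.

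If severity is left out, a larger or more professional network can look harmful, or a real benefit can be hidden. These models serve the Protocol's secondary objective on mechanism (Protocol 1.0). The network functions they flag as important are also the ones carried into the dyad-level analyses, so an error would be passed on.

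**Working it through.** **Inputs from the documents.** Protocol 5.0 plans 106 caregivers with 25% attrition: 106 × (1 − 0.25) = 79.5, about 80, which reproduces its figure. I use n = 80. It is a planning figure, and the SAP gives none of its own. The 84% power in the same section concerns the comparison of arms. It cannot be reproduced because no SD or alpha is given, and nothing here rests on it.

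**Inputs that are assumptions.** Let *a* be the correlation of severity with a network measure and *b* its correlation with the outcome. The documents give neither, so I show a range. The true network effect is set to zero. The model is linear with one network predictor, tested two-sided at 5%.

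**Step 1: bias without severity.** If network and outcome are linked only through severity, their expected correlation is r = a × b.

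**Step 2: false-positive rate.** By Fisher's z the test statistic is centred on atanh(r) × √(80 − 3) = atanh(r) × 8.775. The rejection rate is the probability that a unit normal with that mean falls beyond ±1.96. For a = b = 0.3: r = 0.09, atanh(0.09) = 0.0902, mean 0.79, and the rate is P(Z > 1.17) + P(Z < −2.75) = 0.121 + 0.003 = 12%.

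**Step 3: check by simulation.** 20,000 data sets of 80 caregivers were fitted without severity, then with a severity score of reliability 1.0 or 0.7.

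| a / b | spurious r | mean of z | no severity, Fisher z | no severity, simulated | adjusted, reliability 1.0 | adjusted, reliability 0.7 |
|---|---|---|---|---|---|---|
| 0.1 / 0.1 | 0.01 | 0.09 | 5% | 5% | 5% | 5% |
| 0.2 / 0.2 | 0.04 | 0.35 | 6% | 6% | 5% | 5% |
| 0.3 / 0.3 | 0.09 | 0.79 | 12% | 12% | 5% | 6% |
| 0.4 / 0.4 | 0.16 | 1.42 | 29% | 30% | 5% | 8% |
| 0.5 / 0.4 | 0.20 | 1.78 | 43% | not run | not run | not run |
| 0.5 / 0.5 | 0.25 | 2.24 | 61% | 61% | 5% | 13% |

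With a = 0 and b = 0.3 there is no bias, and the simulated rate is 5%.

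**Step 4: residual bias with an imperfect score.** With reliability ρ, the adjusted slope is ab(1 − ρ)/(1 − ρa²). At a = b = 0.4 and ρ = 0.7 this is 0.16 × 0.3/(1 − 0.112) = 0.054, against 0.16 unadjusted; the simulation gave the same. About two thirds of the bias is removed.

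**Step 5: function-change models.** Baseline severity may be only weakly related to a change score. With a = 0.1 and b = 0.3, r = 0.03, the mean is 0.26, and the rate is P(Z > 1.70) + P(Z < −2.22) = 0.045 + 0.013, about 6%.

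**The case against.** The strongest reply is that the SAP is silent on covariates and does not exclude them. It names the exposures of interest and speaks of associations. A reader might infer that severity has been ruled out and that the results will be misread. The documents do not support that: the fault is a failure to pre-specify, and the bias is possible, not certain. Silence still matters. The revised plan is dated January 2022, data collection was planned to end in March 2021 (Protocol 2.0), and a covariate left open can be chosen after the results are seen.

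A reader might also take the larger percentages as the expected error. Every correlation is assumed, and at 0.2 or below almost nothing happens. Protocol 5.3 limits the sample to recent diagnoses and excludes mild cognitive impairment and residents of care settings, which may narrow the range of severity. Appendix B, however, allows 24 months since diagnosis where 5.3 says 6. Some composition measures, such as the gender or age group of members, have no obvious link to severity. The SAP also enters several measures at once and uses logit or log links for some outcomes, which these figures do not cover.

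A further tempting step is to extend the point to the dyad-level GEE. The example outcomes there are network functions, not burden or emergency care, so the path described above does not apply. Nor do the documents give a basis for requiring recruiting clinic as a covariate on this ground.

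Finally, MoCA is a cognitive score and not a measure of care need, and Protocol 6.1 gives neither its date nor its completeness. Arm and baseline outcome are not named in these GLMs either, and adjusting for baseline burden might absorb part of the confounding. Both remarks stand. They limit what MoCA can do but are not a reason to leave it out.

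**Conclusion.** The point holds for the patient-level GLMs, and mainly for the composition models. As written they relate non-randomised exposures, partly defined by care activity, to burden and emergency care, with no severity term named and a relevant score already collected.

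The size cannot be fixed from the documents. Under the assumptions above the false-positive rate runs from 5-6% at correlations of 0.1 to 0.2, through 12% at 0.3/0.3 and 29-30% at 0.4/0.4, to 43% at 0.5/0.4. For change in network function it is probably nearer the lower end. What is affected is the reading of the secondary mechanism objective. The randomised comparison is untouched. The change should be made, but the trial does not depend on it.

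**What to change.** State in the SAP that the last MoCA recorded before randomisation enters the patient-level GLMs as a covariate: the composition models first, and the function-change models for consistency. A later value should not be used, because the intervention or the changing network could have affected it. Impute a missing MoCA from baseline data so that no caregiver is dropped, and report how many values were imputed.

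The recruitment log is a possible supplement for a sensitivity analysis, since Protocol 12.5 says it "Collects date, age, gender, race, care needs, relationship to PWD, Rural (Y/N". The care-needs item has three levels in Appendix C, but whose needs it rates is not defined.

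The cost is SAP wording and one degree of freedom, with no new data collection. There are two drawbacks. Some records may hold no recent MoCA. An imperfect score also leaves residual confounding: at reliability 0.7, about 6-8% false positives at correlations of 0.3 to 0.4, and 13% at 0.5. The report should therefore still describe these results as associations.
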